# **Amendment 2 DE**

Amendment 2 was a country-specific amendment. All changes made in Amendment 2 were implemented globally in Amendment 3.

# **Amendment 1**

The purpose of this protocol amendment is to correct a typo and provide a clarification within the inclusion criteria.

Description of Change	Rationale	Section Changed
The phrase "augmented rental clearance" was corrected to say "allergic rhinoconjunctivitis."	Correction of a typo.	Section 7.2.1 Inclusion Criteria, #5
A clarification was made that, for adolescents, a parent or legal guardian must also provide informed consent.	For clarification.	Section 7.2.1 Inclusion Criteria, #7 Table 3 Schedule of Events
Additionally, the row for "informed consent" was modified to say "informed consent/assent" within the schedule of events table.		

# **CLINICAL STUDY PROTOCOL SYNOPSIS**

Title	A Randomized, Double-Blind, Placebo-Controlled Study in Cat-Allergic Patients with Allergic Rhinitis Who Live with a Cat to Assess the Efficacy and Safety of Anti-Fel d 1 Antibodies during Natural Cat Exposure in the Home	
Site Locations	Approximately 630 adult and adolescent patients will be enrolled at multiple sites across North America and Europe.	
Principal Investigator	To be determined	
Objectives	Primary Objective	
	The primary objective of the study is to determine the efficacy of REGN1908-1909, as compared to placebo, to reduce allergic rhinitis/conjunctivitis symptoms and allergy rescue medication use during natural cat exposure.	
	Note: The combined symptom and medication score (CSMS) is defined as the daily combined allergic rhinitis and conjunctivitis total symptom score (TSS: calculated as the sum of total nasal symptom score [TNSS] and total ocular symptom score [TOSS]) plus daily medication score (DMS).	
	Secondary Objectives	
	The secondary objectives are:	
	
 
To assess the reduction of allergic symptoms and use of allergy rescue medications after treatment with REGN1908-1909 versus placebo, as measured by the individual components of the CSMS
 
	
	
 
To assess health-related quality of life (HRQoL) as measured by the Rhinoconjunctivitis Quality of Life Questionnaire (RQLQ[S])
 
	
	
 
To determine the efficacy of REGN1908-1909, as compared to placebo, to inhibit a wheal-and-flare response to a skin prick test with cat allergen
 
	
	
 
To assess the durability of effect in allergic rhinitis and conjunctivitis symptom and medication scores after multiple doses of REGN1908- 1909 compared to placebo given every 12 weeks (Q12W)
 
	
	To determine the efficacy following multiple doses of REGN1908-1909 compared to placebo at inhibiting a wheal-and-flare response to a skin prick test with cat allergen	
	To estimate the effect of REGN1908-1909 on lung function, as compared to placebo, in patients with asthma	
	
 
To determine the efficacy of REGN1908-1909 as compared to placebo to reduce asthma symptoms in patients with asthma
 
	

compared to placebo

• To assess whether there is a difference in asthma rescue medication use in patients with asthma who are treated with REGN1908-1909

- To assess whether there is a difference in nighttime awakenings in patients with asthma treated with REGN1908-1909 compared to placebo
- To evaluate the short-term and long-term safety and tolerability of REGN1908-1909, including the incidence of hypersensitivity reactions, local injection site reactions, and asthma exacerbations
- To determine systemic exposure of total (free and antigen-bound) antibodies as measured by concentration of REGN1908 and REGN1909
- To assess the immunogenicity of REGN1908 and REGN1909

# **Study Design**

This is a phase 3, randomized, double-blind, parallel-group, multi-dose study in approximately 630 cat-allergic adult ( $\geq$ 18 years of age) and adolescent patients (ages  $\geq$ 12 to <18 years), where permitted, with allergic rhinitis with or without conjunctivitis and with or without asthma.

- Cat allergic patients living with a cat who are significantly symptomatic while using standard of care anti-allergy medications will be enrolled in the study. The study includes a screening period of up to 12 weeks to ensure sensitization and medication use requirements are met during the baseline period.
- Randomization to 1 of 2 treatment arms (1:1)
  - o REGN1908-1909 600 mg (300 mg per monoclonal antibody [mAb])
  - o Placebo that replaces REGN1908-1909
- Study drug will be administered Q12W for a total of 5 administrations
- End of treatment visit at week 60
- End of study safety follow-up visit at week 72

The screening period is set up to be a long enough duration so that the baseline assessment will occur outside of relevant pollen seasons for patients who are pollen allergic. Efficacy assessments will be done during the initial 12 weeks (weeks 0 to 12) after the first dose and during the last 12-week period (weeks 48 to 60) after last dose (dose 5) of REGN1908-1909 or placebo. For those individuals with seasonal allergies, efficacy assessments will be timed by the investigational site to ensure that the assessments are outside of any relevant pollen seasons.

#### **Study Duration**

The duration of the study for a patient is approximately 72 weeks, excluding the screening period of up to 12 weeks.

## **End of Study Definition**

The end of study is defined as the date the last patient completes the last study visit or withdraws from the study, or is lost to follow-up (ie, the study patient can no longer be contacted by the investigator).

## **Target Population**

Male and female patients 12 years of age and older (≥12 to <18 years of age, where permitted) living with at least 1 cat who have allergic rhinitis with or without conjunctivitis symptoms and with or without asthma with cat sensitization confirmed at screening will be enrolled after they meet a symptom and medication requirement at baseline. Other inclusion and exclusion criteria apply.

## Sample Size:

Approximately 630 patients will be enrolled.

#### **Treatment**

Study Drug and Placebo Dose/Route/Schedule:

- REGN1908-1909 600 mg (300 mg per mAb), administered by subcutaneous (SC) injections Q12W for a total of 5 doses
- Matching placebo that replaces REGN1908-1909 SC Q12W

### **Endpoints**

### **Primary Endpoint**

The primary endpoint is the daily CSMS, averaged over the last 12 weeks of the treatment period (weeks 48 to 60), in patients who receive REGN1908-1909 versus placebo.

Note: CSMS is defined as the daily combined allergic rhinitis and conjunctivitis TSS (calculated as the sum of TNSS and TOSS) plus daily medication score (DMS).

### **Key Secondary Endpoints**

The key secondary endpoints, specified without order, are:

- Daily TNSS, averaged over the last 12 weeks of treatment period (weeks 48 to 60), in patients who receive REGN1908-1909 versus placebo
- Percent change from pre-treatment baseline in average CSMS, over the last 12 weeks of the treatment period (weeks 48 to 60), in patients who receive REGN1908-1909 versus placebo
- Percent change from pre-treatment baseline in average TNSS, over the last 12 weeks of the treatment period (weeks 48 to 60), in patients who receive REGN1908-1909 versus placebo
- Daily TSS, averaged over the last 12 weeks of the treatment period (weeks 48 to 60), in patients who receive REGN1908-1909 versus placebo
- Percent change from pre-treatment baseline in average TSS, over the last 12 weeks of the treatment period (weeks 48 to 60), in patients who receive REGN1908-1909 versus placebo
- Percent change from baseline to the end of treatment (week 60) in cat SPT mean wheal diameter in patients who receive REGN1908-1909 versus

# **Other Secondary Endpoints**

Other secondary endpoints, specified without order, are:

- Daily CSMS, averaged over the initial 12 weeks of the treatment period (weeks 0 to 12), in patients who receive REGN1908-1909 versus placebo
- Daily TNSS, averaged over the initial 12 weeks of treatment period (weeks 0 to 12), in patients who receive REGN1908-1909 versus placebo
- Percent change from pre-treatment baseline in average CSMS, over the initial 12 weeks of the treatment period (weeks 0 to 12), in patients who receive REGN1908-1909 versus placebo
- Percent change from pre-treatment baseline in average TNSS, over the initial 12 weeks of the treatment period (weeks 0 to 12), in patients who receive REGN1908-1909 versus placebo
- Percent change from pre-treatment baseline in average TSS, over the initial 12 weeks of the treatment period (weeks 0 to 12), in patients who receive REGN1908-1909 versus placebo
- Daily TSS score, averaged over the initial 12 weeks of the treatment period (weeks 0 to 12), in patients who receive REGN1908-1909 versus placebo
- Percent change from pre-treatment baseline in average TOSS, over the initial 12 weeks of the treatment period (weeks 0 to 12), in patients who receive REGN1908-1909 versus placebo
- Daily TOSS, averaged over the last 12 weeks of the treatment period (weeks 48 to 60), in patients who receive REGN1908-1909 versus placebo
- Percent change from pre-treatment baseline in average TOSS, over the last 12 weeks of the treatment period (weeks 48 to 60), in patients who receive REGN1908-1909 versus placebo
- Percent change from baseline to week 12 in FEV1 in patients with asthma who receive REGN1908-1909 versus placebo
- Percent change from baseline to week 60 in FEV1 in patients with asthma who receive REGN1908-1909 versus placebo
- Percent change from baseline to week 12 in cat skin prick test (SPT) mean wheal diameter in patients who receive REGN1908-1909 versus placebo
- Change from baseline to week 12 in FEV1 in patients with asthma who receive REGN1908-1909 versus placebo
- Change from baseline to week 60 in FEV1 in patients with asthma who receive REGN1908-1909 versus placebo
- Change from baseline to week 60 in RQLQ(S)+12 in patients who receive REGN1908-1909 versus placebo
- DMS, averaged over the initial 12 weeks of the treatment period (weeks 0 to 12), in patients who receive REGN1908-1909 versus placebo

- DMS, averaged over the last 12 weeks of the treatment period (weeks 48 to 60), in patients who receive REGN1908-1909 versus placebo
- Percent change from pre-treatment baseline in average DMS, averaged over the last 12 weeks of the treatment period (weeks 48 to 60), in patients who receive REGN1908-1909 versus placebo
- Percent change from baseline to end of study (week 72) in cat SPT mean wheal diameter in patients who receive REGN1908-1909 versus placebo
- Asthma daily symptom (ADS) score, averaged over the initial 12 weeks of the treatment period (weeks 0 to 12), using Asthma Daytime Symptom Diary (ADSD) and the Asthma Nighttime Symptom Diary (ANSD), in patients with asthma who receive REGN1908-1909 versus placebo
- Asthma daily symptom (ADS) score, averaged over the last 12 weeks of the treatment period (weeks 48 to 60), using Asthma Daytime Symptom Diary (ADSD) and the Asthma Nighttime Symptom Diary (ANSD), in patients with asthma who receive REGN1908-1909 versus placebo
- Daily TOSS, averaged over the initial 12 weeks of the treatment period (weeks 0 to 12), in patients who receive REGN1908-1909 versus placebo
- Change from baseline to week 60 in ACQ-5 in patients with asthma who receive REGN1908-1909 versus placebo
- Daily number of nighttime awakenings, averaged over the initial 12 weeks of the treatment period (weeks 0 to 12), in patients with asthma who receive REGN1908-1909 versus placebo
- Daily number of nighttime awakenings, averaged over the last 12 weeks of the treatment period (weeks 48 to 60), in patients with asthma who receive REGN1908-1909 versus placebo
- Incidence of treatment-emergent adverse events (TEAEs), AESIs, and serious TEAEs throughout the study (weeks 0 to 72)
- Total REGN1908 and REGN1909 concentration in serum over the study duration (weeks 0 to 72)
- Incidence of treatment-emergent anti-drug antibodies (ADAs) to REGN1908 and REGN1909 throughout the study (weeks 0 to 72)

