A statement was added noting that anaphylaxis will be prospectively analyzed using the criteria discussed in the statement paper from the Second	This statement and reference were added based on health authority suggestion.	Section 10.1.3 Events that Require Expedited Reporting to the Sponsor

Description of Change	Brief Rationale	Sections Changed
Symposium on the definition and Management of Anaphylaxis (Summary Report-Second National Institute of Allergy and Infectious Disease/Food Allergy and Anaphylaxis Network Symposium. J Allergy Clin Immunol 2006;117(2):391-97).		
Exclusion criterion number 13 was modified to "SIT with any allergen other than cat at screening visit 1. Patients who plan to initiate SIT during the trial period will be excluded." The prior criterion excluded patients on SIT with any allergen other than cat within 6 months prior to screening visit 1.	This change was made to allow more flexibility for patients to enroll in the trial if they were not on allergen specific immunotherapy other than cat at screening visit 1 without the requirement for a 6-month washout prior to screening, based on health authority feedback.	Section 7.2.2 Exclusion Criteria, criterion #13
Treatment-emergent adverse events (TEAEs) will be defined as those that are not present at baseline or represent the exacerbation of a pre-existing condition during the on-treatment and follow-up periods.	This definition within the safety analysis section was updated to align with the endpoints.	Section 11.4.6.1 Adverse Events
The 3 locations for subcutaneous (SC) injection (upper arms, abdomen, and thighs) for a single dose was added to the description of investigational treatments, along with the recommendation not to administer all 3 injections in the same site. A statement that there will be 5 visits during the treatment period during which study drug will be administered for a total of 15 injections was also added.	Additional instructional and descriptive information regarding study drug administration was provided in the protocol for convenience and clarity.	Section 8.1 Investigational and Reference Treatments

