# 8.3.2. Study Drug Discontinuation

Patients who permanently discontinue from study drug should be encouraged to remain in the study. Those who agree and do not withdraw from the study will be asked to return to the clinic for all remaining study visits per the visit schedule.

Patients who permanently discontinue from study drug and who opt to withdraw from the study will be asked to complete study assessments, per Section 9.1.2.

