#### 11.4.6.1. Adverse Events

#### **Definitions**

For safety variables, 3 observation periods are defined:

- The pretreatment period is defined as the time from signing the ICF to before the first dose of study drug.
- The on-treatment period is defined as the day from first dose of study drug to the last dose of study drug plus 12 weeks (weeks 0 to 60).
- The follow-up period is defined as the end of the on-treatment period to 12 weeks after the end of the on-treatment period (weeks 60 to 72).

Treatment-emergent adverse events are defined as those that are not present at baseline or represent the exacerbation of a pre-existing condition during the on-treatment and follow-up periods.

Adverse events of special interest (Section 10.2.3 and Section 10.1.3) for this study include:

- Severe or systemic hypersensitivity reactions defined using the narrow SMQ for hypersensitivity, with manual adjudication of relevant PTs by medical monitor before database lock.
- Asthma exacerbations defined using the narrow SMQ for asthma and further manually adjudicated for events requiring treatment with systemic corticosteroids or resulting in an emergency room visit or hospitalization.

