4.6. Safety Variables

4.6.1. Adverse Events and Serious Adverse Events

Adverse events and serious adverse events will be collected from the time of informed consent signature and then at each visit until the end of the study. All adverse events are to be coded to a “Preferred Term (PT)” and associated primary “System Organ Class (SOC)” according to the Medical Dictionary for Regulatory Activities (MedDRA).

An Adverse Event is any untoward medical occurrence in a patient administered a study drug which may or may not have a causal relationship with the study drug. Laboratory results, vital signs, or ECG abnormalities are to be recorded as AEs if they are medically relevant: symptomatic, requiring corrective therapy, leading to treatment discontinuation and/or fulfilling a seriousness criterion.

For safety variables, 4 observation periods are defined:

- The pretreatment period is defined as the time from signing the ICF to before the first dose of study drug.
- The on-treatment period is defined as the day from first dose of study drug to the last dose of study drug plus 12 weeks (visit 3 to visit 14).
- The follow-up period is defined as the end of the on-treatment period to 12 weeks after the end of the on-treatment period (visit 14 to visit 15).
- The overall study period is defined as the day from first dose of study drug to the end of study visit (on-treatment period plus follow-up period)

Treatment-emergent adverse events (TEAEs) are defined as those that are not present at baseline or represent the exacerbation of a pre-existing condition during the on-treatment and follow-up periods.

A Serious Adverse Event is an adverse event (AE) that is classified as serious according to the criteria specified in the study protocol 10.2.2.

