5.7. Analysis of Safety Data

The analysis of safety will be performed on the SAF, as defined in Section [3.2](#).

The safety analysis will be based on the reported AEs and other safety information (clinical laboratory evaluations, and vital signs).

Thresholds for treatment-emergent Potential Clinically Significant Values (PCSV) in laboratory variables and vital signs are defined in Section [10.3](#). Treatment-emergent PCSV is any PCSV that developed or worsened in severity compared to the baseline during the on-treatment and follow-up period. The baseline when determining treatment-emergent PCSV refers to the baseline value of the study.

The summary of safety results will be presented for each treatment group. The time interval to detect any event or abnormality is between the first injection of study medication and EOS.

In addition, the summary of safety results (including TEAEs, clinical laboratory, vital signs, and ECG) will be performed for subjects who were impacted by COVID-19 pandemic and not impacted by COVID-19 pandemic in each study part, respectively if deemed appropriate. The summary will be performed for pre-, during, and post-COVID-19 periods for patients impacted by COVID-19, if deemed appropriate.

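### The TEAE window has two anchors that agree only for patients who receive all five doses; for patients who stop drug early and stay in the study, the dose-based anchor closes it 12 to 48 weeks before week 72

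*Protocol*

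**What the plan says.** The endpoint, listed in the Synopsis and Protocol 4.2 among the unordered other secondary endpoints, is "Incidence of treatment-emergent adverse events (TEAEs), AESIs, and serious TEAEs throughout the study (weeks 0 to 72").

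Protocol 11.4.6.1 restricts TEAEs to two periods. The on-treatment period is "the day from first dose of study drug to the last dose of study drug plus 12 weeks (weeks 0 to 60"). Then: "The follow-up period is defined as the end of the on-treatment period to 12 weeks after the end of the on-treatment period", which the same sentence labels weeks 60 to 72. SAP 4.6.1 repeats both dose-based definitions but labels them visits 3 to 14 and visits 14 to 15. It adds a fourth period: "The overall study period is defined as the day from first dose of study drug to the end of study visit", and equates this with the on-treatment and follow-up periods added together.

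SAP 5.7 limits treatment-emergent PCSVs to the on-treatment and follow-up periods, and then says: "The time interval to detect any event or abnormality is between the first injection of study medication and EOS".

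Protocol 8.3.2 encourages patients who permanently stop drug to remain in the study. Those who agree "will be asked to return to the clinic for all remaining study visits per the visit schedule". Protocol 9.1.2 says the same.

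On collection, Protocol 10.1.1 has events recorded from consent to the end of the on-treatment period, after which only SAEs judged related are to be reported. SAP 4.6.1 has AEs collected at each visit until the study ends.

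For time-to-event analyses, Protocol 11.4.6.1 and SAP 5.7.1 take selected events within the 60-week treatment period and censor event-free patients at the end of the study period.

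**The concern.** The design keeps patients who have stopped drug under observation to week 72. It therefore creates the group for whom the dose-based limit and the fixed label fall on different dates. Two programmers who both follow the text could report different TEAE, AESI and PCSV counts from one database.

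The by-period tables in SAP 5.7.1 are affected as well as the overall total. Take a patient who stops after dose 1 and has an event at week 40. By the labels it belongs to the 60-week treatment period. By the dose rule it is in neither the on-treatment nor the follow-up period.

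The SAP offers no tie-breaker for AEs. Section 5.7.1 refers the reader to Section 3.2 for the TEAE search criteria, but 3.2 defines the safety analysis set and contains no window. For concomitant medications, by contrast, SAP 4.3 does fix the boundary: the week 60 visit date, or day 421 if that is missing.

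**Working it through.** **Inputs.** Doses every 12 weeks for five administrations, so on days 1, 85, 169, 253 and 337 (weeks 0, 12, 24, 36, 48); end-of-study visit on day 505 (week 72) (Protocol Table 3). Each of the two periods adds 12 weeks, or 84 days (Protocol 11.4.6.1).

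**The plan's own labels.** Last dose at week 48: on-treatment ends at 48 + 12 = week 60, and follow-up ends at 60 + 12 = week 72. Both labels reproduce for a patient who receives all five doses on schedule.

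**Dose-based wording for everyone else.** End of TEAE window = week of last dose + 24. Gap = 72 - (week of last dose + 24).

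| Last dose | Week | On-treatment ends | TEAE window ends | Gap to week 72 | Share of 72 weeks |
|---|---|---|---|---|---|
| 1 | 0 | 12 | 24 | 48 weeks | 67% |
| 2 | 12 | 24 | 36 | 36 weeks | 50% |
| 3 | 24 | 36 | 48 | 24 weeks | 33% |
| 4 | 36 | 48 | 60 | 12 weeks | 17% |
| 5 | 48 | 60 | 72 | 0 | 0% |

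**Fixed labels, or SAP 5.7's interval.** The window runs to week 72 (visit 15), so the gap is 0 for every patient who stays.

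**The SAP's equation.** For a patient with dose 1 only, first dose to the end-of-study visit is 72 weeks, while dose-based on-treatment plus follow-up is 12 + 12 = 24 weeks. The two are equal only in the last row of the table.

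**Size in an arm (illustration, not from the documents).** Suppose 10% of an arm stops at a given dose and everyone is followed to week 72. The uncovered share of the arm's follow-up is 10% x gap/72: 6.7%, 5.0%, 3.3% or 1.7% for last dose 1, 2, 3 or 4. It scales in proportion to the assumed 10%.

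**Censoring.** If every patient's events are counted to week 60, censoring at week 60 or week 72 gives the same risk sets at every event time, so the hazard ratio is unchanged. If the window closes at last dose + 24 weeks, it does matter. A patient with dose 1 only stays in the risk set from week 24 to week 60, which is 36 weeks in which no event could be scored for that patient. For last dose 2 and 3 the figures are 60 - 36 = 24 and 60 - 48 = 12 weeks.

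**Recording.** Under Protocol 10.1.1 routine recording ends with the on-treatment period. By the fixed label that is week 60, which is 12 weeks short of the endpoint for every patient. By the dose rule it is 72 - 12 = 60 weeks short for a patient with dose 1 only.

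**The case against.** A reader might infer that late events in early stoppers belong to no period at all. The documents do not support that. The SAP's overall study period and its first-injection-to-end-of-study interval both cover them, and SAP 5.7.1 tabulates TEAEs over the whole study.

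Nor is it settled that the window closes at last dose + 24 weeks, because the same sentences carry labels running to week 72. The Amendment 3 history says of the TEAE definition: "This definition within the safety analysis section was updated to align with the endpoints". That is rationale text rather than a rule, but it suggests weeks 0 to 72 was intended.

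A dose-based window would also be defensible in itself. With half-lives of 31.0 and 22.4 days (Protocol 3.2.2), 168 days is 168/31.0 = 5.4 and 168/22.4 = 7.5 half-lives, and pregnancy reporting also uses 24 weeks after the last dose.

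The consequences have limits too. This is one of many other secondary endpoints, safety analysis is descriptive, and the SAP makes the hazard ratios optional.

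All of this stands. It shows that the plan contains competing rules, not that it chooses between them. The TEAE definition itself still points to the two periods, and taken at its dose-based wording it leaves out events that the endpoint says it counts.

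**Conclusion.** The point holds as an unresolved contradiction in the TEAE definition. For patients who stop drug early and remain in the study, the window closes 48, 36, 24 or 12 weeks before week 72 under the dose-based wording, and at week 72 under the labels. Under the dose-based wording, the SAP's equation of the overall study period with on-treatment plus follow-up is false for these patients. The same ambiguity reaches treatment-emergent PCSVs and the by-period AE tables.

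The figures assume scheduled dosing days and a patient who stays to week 72. The documents do not give the number of patients who stop drug and stay; the 20% dropout assumption does not supply it. It is tempting to add that the missing events would cluster in patients who stopped for tolerability, or would differ by arm. Nothing in the documents shows either. No power or alpha figure is affected.

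**What to change.** In Protocol 11.4.6.1 and SAP 4.6.1:

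- Define the TEAE window for every treated patient as first dose to that patient's last study visit, to match the weeks 0-72 endpoint. Use the same window for treatment-emergent PCSVs in SAP 5.7.
- Keep on-treatment as first dose to last dose + 84 days, and let follow-up run from then to the last visit. The SAP's statement that the two make up the overall study period then becomes true.
- State that the bracketed weeks and visits describe patients who receive all five doses, and align the period names in SAP 5.7.1.
- Censor time-to-event analyses (Protocol 11.4.6.1, SAP 5.7.1) at the end of the window in which events are counted.
- Correct the SAP 5.7.1 reference to Section 3.2.
- Reconcile Protocol 10.1.1 with SAP 4.6.1 on how long AEs are recorded.

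Most of this costs definition wording and one derivation in the AE data set, settled before unblinding. The last item may cost more: if sites stopped routine recording at the end of the on-treatment period, later events may not be in the data and no derivation can recover them.
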